Appendix 10: Adverse Event Form

STUDY NAME

Site Name: _____ Pt_ID: _____	This form is cumulative and captures adverse events of a single participant throughout the study.
-------------------------------------	---

Severity	Study Intervention Relationship	Action Taken Regarding Study Intervention	Outcome of AE	Expected	Serious Adverse Event (SAE)
1 = Mild 2 = Moderate 3 = Severe 4 = Life-Threatening	0 = Not related 1 = Unlikely related 2 = Possibly related 3 = Probably related 4 = Definitely related	0 = None 1 = Dose modification 2 = Medical Intervention 3 = Hospitalization 4 = Intervention discontinued 5 = Other	1 = Resolved 2 = Recovered with minor sequelae 3 = Recovered with major sequelae 4 = Ongoing/Continuing treatment 5 = Condition worsening 6 = Death 7 = Unknown	1 = Yes 2 = No	1 = Yes 2 = No (if yes, complete SAE form)

At end of study only: Check this box if participant had no adverse events None

Adverse Event	Start Date	Stop Date	Severity	Relationship	Action Taken	Outcome of AE	Expected ?	SAE?

Appendix 11: Unanticipated Problem (UP)

Protocol Name and Number:	Site Name:	Subject ID Number or List of Affected Subjects:
_____	_____	_____

1. Date UP Identified: ___/___/___ (dd/mmm/yyyy)
2. Identify UP: _____
3. The Unanticipated Problem was unexpected in terms of nature, severity, or frequency: Yes No
4. The Unanticipated Problem is possibly related to participation in the research: Yes No
5. The Unanticipated Problem suggests that the research places subjects or others at a greater risk of harm than was previously known or recognized: Yes No

If the answers to questions 3–5 are ALL “YES,” report event as an Unanticipated Problem to NCCIH and the institutional review board (if applicable).

6. Briefly describe the UP. Attach additional pages or supplementary information as necessary. Include date of incident and date of discovery. Describe harm or potential harm that occurred to subject(s), whether the incident is resolved, and whether the subject(s) remains in the study:

7. What action was taken with the study as a result of the Unanticipated Problem? (Check all that apply.)

 No action  Revise protocol to eliminate apparent immediate hazards to subjects  Modification of inclusion or exclusion criteria to mitigate newly identified risks  Implementation of additional procedures for monitoring subjects  Suspension of enrollment of new subjects  Notify currently enrolled subjects	 Suspension of research procedures in currently enrolled subjects  Modification of consent documents to include a description of newly recognized risks (site and/or study wide)  Provision of additional information about newly recognized risks to previously enrolled subjects  Other: _____
---	---

8. Is the Unanticipated Problem a serious adverse event?

Yes No

If the Unanticipated Problem is a serious adverse event, submit this form and complete the Serious Adverse Event form.

Statement of Principal Investigator: *I have personally reviewed this report and agree with the above assessment.*

Signature of Principal Investigator

___/___/_____
Date

Name of Person Completing the Form

___/___/_____
Date

Appendix 12: Serious Adverse Event Form

STUDY NAME

Protocol Number: _____

Site Name: _____

Pt ID: _____

Date Participant Reported:

____/____/_____
d d m m m y y y y

1. SAE onset date: ____/____/_____
d d m m m y y y y

2. SAE stop date: ____/____/_____
d d m m m y y y y

3. Location of SAE: _____

4. Was this an unexpected adverse event? Yes No

5. Brief description of participants with no personal identifiers:

Sex: F M Age: _____

Diagnosis for study participation: _____

6. Brief description of the nature of the SAE (attach description if more space is needed):

7. Category of the SAE:

Date of death ____/____/_____
(dd/mmm/yyyy)

Life threatening

Hospitalization – initial or prolonged

Disability/incapacity

Congenital anomaly/birth defect

Required intervention to prevent permanent impairment

Other: _____

8. Intervention type:

- Medication or nutritional supplement (specify): _____
- Device (specify): _____
- Surgery (specify): _____
- Behavioral/lifestyle (specify): _____

9. Relationship of event to intervention:

- Unrelated (clearly not related to the intervention)
- Possible (may be related to intervention)
- Definite (clearly related to intervention)

10. Was study intervention discontinued due to event? Yes No

11. What medications or other steps were taken to treat the SAE?

12. List any relevant tests, laboratory data, and history, including preexisting medical conditions:

13. Type of report:

- Initial
- Follow-up
- Final

Signature of principal investigator: _____ Date: _____

Appendix 13: Participant Eligibility Checklist

Participant Name _____

Date: _____

Please check the box for all inclusion criteria satisfied.

Inclusion Criteria Satisfied:

- Male or female 18-45 years of age
- History of ankle sprain with at least two episodes of “giving way” within the past six months
- Score of ≥ 5 on the Ankle Instability Instrument (All)
- Score of $\leq 90\%$ on the FAAM-ADL
- Score of $\leq 80\%$ on the FAAM-S.

Notes about inclusion criteria:

Exclusion Criteria Triggered:

- Younger than 18 or older than 45 years
- No history of ankle sprain or episodes of “giving way” in the past six months
- Score of ≤ 5 on the Ankle Instability Instrument (All)
- Score of $\geq 90\%$ on the FAAM-ADL
- Score of $\geq 80\%$ on the FAAM-S.
- An acute ankle sprain within the past 6 weeks.
- Previous history of lower extremity surgery with internal derangements, reconstructions, or repair
- Lower extremity injury within the past 6 months (other than ankle sprains)
- Presence of balance deficits or conditions known to affect balance as noted on the Balance Questionnaire including diabetes and/or vertigo.

Notes about exclusion criteria:

If all inclusion criteria are satisfied (all boxes checked) and none of the exclusion criteria are triggered, then the participant can be enrolled in the study. If not all inclusion boxes are checked or one or more of the exclusion boxes are checked, participation in this study is no longer allowed.

Screener Name: _____

Screener Signature: _____

Date: _____

PI Signature: _____

Date: _____

Gender and Racial/Ethnic Categories of participant if eligible for inclusion into the study:

Please circle the gender and racial/ethnic categories of the potential participant:

Gender: Male Female

Ethnicity: Hispanic/Latino Not Hispanic/Latino

Race: Asian Black/African American White

American Indian/Alaska Native Native Hawaiian or Other Pacific
Islander

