Inclusion Criteria (per Appendix 13): Males and females between the ages of 18 and 45 with self-reported CAI; defined as self-reported episodes of recurrent ankle sprains and/or the feeling of instability or “giving way” after an initial ankle sprain. Inclusion criteria will consist of a history of at least two episodes of “giving way” within the past 6 months; answering 5 or more questions of “Yes” on the Ankle Instability Instrument (All) (Appendix 2); a score of <90% on the self-reported Foot and Ankle Ability Measure (FAAM); a score of <80% on the FAAM Sport (Appendix 3 & 4).

Exclusion Criteria (per Appendix 13): Exclusion criteria will consist of failing to meet the inclusion criteria as well as reporting an acute ankle sprain within the past 6 weeks; a previous history of ankle surgeries; lower extremity surgeries associated with internal

SECTION F: Recruitment, Screening, & Eligibility Criteria

derangements, reconstructions, or repairs; lower extremity injuries within the past 6 months (other than ankle sprains); and balance deficits, neuropathies or other disorders or conditions known to affect balance.

Each investigator who evaluates the eligibility of a potential participant will complete an eligibility checklist (Appendix 13) to determine whether the participant fits the inclusion criteria for the study. The investigator is required to check the appropriate boxes, identify and mark the relevant gender and racial/ethnic information (once eligibility is determined), and sign and date the checklist. The PI will then sign the form as well.

SECTION G: Informed Consent & HIPAA

G.1 Informed Consent Process

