Interested participants will be asked to fill out on-line questionnaires regarding their age, history of ankle injury (All), ankle function (FAAM, FAAM-S), and any balance issues to determine eligibility for participation in the study (Appendix 2-4). To be eligible, individuals must meet the following criteria as outlined in section 7 of Appendix 1 and section F.4 of the MOOP. In addition, participants will complete three 1-item questionnaires related to their expectations of treatment efficacy (Appendix 5). These responses will be used to match participants based on their expectations of the treatments to be provided.

Males and females between the ages of 18 and 45 with self-reported CAI; defined as self-reported episodes of recurrent ankle sprains and/or the feeling of instability or “giving way” after an initial ankle sprain. Inclusion criteria will consist of a history of at least two episodes of “giving way” within the past 6 months; answering 5 or more questions of “Yes” on the Ankle Instability Instrument (All); a score of < 90% on the self-reported Foot and Ankle Ability Measure (FAAM); a score of < 80% on the FAAM Sport. Exclusion criteria will consist of reporting an acute ankle sprain within the past 6 weeks; a previous history of ankle surgeries; lower extremity surgeries associated with internal derangements, reconstructions, or repairs; lower extremity injuries within the past 6 months (other than ankle sprains); and balance deficits, neuropathies or other disorders or conditions known to affect balance.

**If a participant is determined to be ineligible for the investigation, then the data collected (to determine eligibility) will be immediately destroyed. Specifically, the All, balance questionnaire, FAAM, and FAAM-S, data sheets must be shredded immediately. No other data can be collected prior to the participant reading and signing the informed consent document.

K.2.b Visit 1:

Informed Consent Process

Once eligible, participants will be schedule to report to the research laboratory of the PI at their respective institution. Once there, eligible participants will first read and sign the informed consent document as outlined in section H. Information will then be collected regarding height, leg length, foot measurements, and weight (see Appendix 17) as well as physical activity and overall function (see Appendix 3 & 4). Height, leg length, and

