Participants will be randomized to one of groups in a 1:1:1 ratio after stratification based on treatment expectation responses. This process will happen using sealed envelopes prepared by the study biostatistician. More specifically, we will be using a block randomization technique at each institution so that preliminary data analysis, data monitoring, and safety evaluations will be based on similar, if not identical, numbers in each group. Each block of envelopes will be made and sealed before study enrollment begins and randomization will occur after the baseline evaluation (see section 9.b below). The biostatistician will be responsible for generating the master randomization list and each participant will select a sealed envelope containing their group assignment. This assignment will be noted by the PI and recorded. Assessors will be blinded to group assignment.

9 Screening Process, Baseline Evaluation, Study Treatment, & Final Evaluation

9.a Screening Process

The screening process will be performed at a specific eligibility screening session. At this session, potential participants will complete the Balance Questionnaire (Appendix 2), All (Appendix 3), FAAM (Appendix 4), FAAM-Sport (Appendix 4), and Treatment Expectation (Appendix 5) questionnaires. If eligible, participants will be scheduled for baseline testing which will be the first of 3 testing sessions. The first will take place on the day of baseline evaluation. The second will take place at the end of the 2-week intervention. The third will take place 1-month after the final treatment session.

9.b Baseline & Post-Test Evaluations

The baseline evaluation will include gathering general information regarding age, height, leg length, foot measurements, weight. Participants will then receive instruction on the testing procedures and will perform several warm-up trials on all assessments to become familiarized with the testing procedures. Next, participants will have their ankle range of motion, postural control, and lower extremity biomechanics tested. Finally, participants will complete the possible neuromuscular mechanism measures. All outcomes will be performed at all test sessions. More detailed descriptions are provided below:

[figure not shown]
Peripheral Neuromuscular Mechanisms:

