Appendix 2: Balance Questionnaire

Participant Number _____ Date _____

Balance History Questionnaire (Version 1, Dec 2017)

1. Have you injured your foot, ankle, knee or hip of either leg in the past six months?
 YES NO
2. Have you ever had surgery on either leg?
 YES NO
3. Have you had an injury or illness that affects your ability to balance in the past six months?
 YES NO
4. Do you presently have a head cold or sinus problems that affect your ability to balance?
 YES NO
5. Do you have any history of Vertigo or balance problems?
 YES NO
6. Do you have any vision problems that affect your ability to balance?
 YES NO
7. Do you have any nerve problems in your legs or any decrease or increase of sensation in your legs or feet?
 YES NO
8. Do you have any history of circulation problems in your legs?
 YES NO
9. Do you have Diabetes?
 YES NO

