Exclusion criteria for CAI will include known vestibular and vision problems, acute lower extremities and head injuries (<6 weeks), chronic musculoskeletal conditions known to affect balance (e.g., ACL deficiency) and a history of ankle surgeries to fix internal derangements. Participants will also be excluded if they have any of the following which are contraindications to TMS testing: metal anywhere in the head (except in the mouth), pacemakers, implantable medical pumps, ventriculo-peritoneal shunts, intracardiac lines, history of seizures, stroke, and serious head trauma. Given the young age (18-35) of the proposed participants, we do not anticipate encountering these conditions but will screen for them non-the-less. The most likely conditions that will be encountered are a history of seizures and history of serious head trauma.

Reference ID: 201657	Date Received: 10/05/2017 08:52:38 PM	Page: 5 of 21
----------------------	---------------------------------------	---------------

IRB Number: 17-2655	Initial	Principal Investigator: [name]
---------------------	---------	---------------------------------------

A.3.2. Justify any exclusion based on race, gender or ethnicity

NA

A.3.3. Will pregnant women or women who become pregnant be excluded?

Yes

If yes, provide justification and describe the type and timing of pregnancy testing to be used:

We will exclude subjects that are known to be pregnant but will not perform pregnancy testing. Pregnancy will be excluded by self reporting from the subject. Pregnant women will be excluded due to the fact that later stages pregnancy impairs postural control. If a woman becomes pregnant while enrolled, she will not be excluded.

A.4. Study design, methods and procedures

Your response to the next question will help determine what further questions you will be asked in the following sections.

A.4.1. Will you be using any methods or procedures commonly used in biomedical or clinical research (this would include but not be limited to drawing blood, performing lab tests or biological monitoring, conducting physical exams, administering drugs, or conducting a clinical trial)?

Yes

A.4.2. Describe the study design. List and describe study procedures, including a sequential description of what subjects will be asked to do, when relevant.

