a waiver of informed consent in its entirety

a waiver or alteration of some of the elements of informed consent

a waiver of HIPAA authorization (If you are accessing patient records for this research, you must also request a waiver of HIPAA authorization)

IRB Number: 17-2655 Initial Principal Investigator: [name]

D.3.2. If your request for a waiver applies to some but not all of your subject groups and/or consent forms, please describe and justify
 No Answer Provided

D.3.3. Does this request for waiver support a study design that involves deception or withholding of information?
 No

Consent Forms

This submission requires the following consent forms

Template Type

Adult Consent Form

Text for Online Consent Form

I am not using this template because: Waiver of written consent requested in application (Section D.2.)

This submission includes the following consent forms

File Name

Adult_Consent_Form-1_BIO of MT_R1.docx

Document Type

Adult Consent Form

[view consent forms](#)

Attachments

This submission requires the following attachments

Document Type

Grant Application

Electronic Questionnaire Survey

Script for Class Recruitment

Flyer for Recruitment

Email or Listserv Recruitment

This submission includes the following attachments

File Name

COMBINED GRANT_NO CITATION FIELDS.docx

Class Recruitment_Bio of MT.docx

Email Recruitment_Bio of MT.docx

Flyer_Bio of MT.docx

Eligibility Packets_Bio of MT.docx

RE R21AT009704-01 clarification letter.txt

Document Type

Grant Application

Script for Class Recruitment

Email or Listserv Recruitment

Flyer for Recruitment

Electronic Questionnaire Survey

Email Correspondence (convert to PDF or TXT)

[view attachments](#)

Addenda

 Data Security Requirements

[view addenda](#)

IRB Number: 17-2655

Initial

Principal Investigator: [name]

If Principal Investigator of this study is a Student or Trainee Investigator, the Faculty Advisor certifies the following:

I accept ultimate responsibility for ensuring that this study complies with all the obligations listed above for the PI.

By certifying below, the Principal Investigator affirms the following:

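### The enrolment checklist names none of the eight TMS contraindications that the IRB protocol excludes, and it refuses an AII score of 5 that the inclusion rule admits

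*Combined protocol and SAP*

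**What the plan says.** Section F.4 states that each investigator who assesses a candidate "will complete an eligibility checklist (Appendix 13) to determine whether the participant fits the inclusion criteria for the study". The form in Appendix 13 has five inclusion lines and nine exclusion lines, matching Appendix 1 Section 7. When all inclusion boxes are checked "and none of the exclusion criteria are triggered, then the participant can be enrolled in the study"; a single checked exclusion box ends participation.

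The IRB protocol (Appendix 18, A.3.1) adds exclusions that the form lacks. It lists "contraindications to TMS testing: metal anywhere in the head (except in the mouth), pacemakers, implantable medical pumps, ventriculo-peritoneal shunts, intracardiac lines, history of seizures", and then stroke and serious head trauma. Of these it says "we do not anticipate encountering these conditions but will screen for them non-the-less", and it names seizure history and serious head trauma as the two most likely to be met.

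Section K.2.a describes the screening instruments as "on-line questionnaires regarding their age, history of ankle injury (All), ankle function (FAAM, FAAM-S), and any balance issues to determine eligibility" (the extracted text prints AII as All). Appendix 1 Section 9.b says "All outcomes will be performed at all test sessions", so TMS is given at baseline, post-test and follow-up.

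On ankle instability, the checklist and Section 7 include an AII score of at least 5 and exclude a score of 5 or below. F.4, K.2.a and Appendix 1 Section 6 admit 5. A.3.1 admits 4.

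**The concern.** The form that decides enrolment and the IRB protocol can give opposite answers for the same person. Under A.3.1 a candidate with a pacemaker or a history of seizures is excluded. On the checklist that candidate triggers no exclusion and can be enrolled, and TMS then follows at the baseline session. The exclusion exists to protect participants from a study procedure, so leaving it off the operative form is a safety gap.

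The AII conflict is of a different kind. It refuses people whom the stated population includes, so the enrolled group is not quite the one described in F.4 and Section 6.

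**Working it through.** No figure in the plan has to be reproduced. The check is a comparison of lists, a boundary test and a count of sessions.

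**TMS contraindications against the screening text.** Each A.3.1 item was looked for in Appendix 13, Appendix 1 Section 7, F.4 and Appendices 2 to 5.

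| A.3.1 exclusion | Named on the checklist or in the screening questionnaires? | Possible indirect route |
|---|---|---|
| Metal in the head | No | None |
| Pacemaker | No | None |
| Implanted pump | No | None |
| Ventriculo-peritoneal shunt | No | None |
| Intracardiac line | No | None |
| Seizure history | No | None |
| Stroke | No | General balance wording |
| Serious head trauma | No | General balance wording |

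- Named: 0 of 8, across 5 + 9 = 14 checklist lines and the 9 Balance Questionnaire items.
- At most 2 of 8 could be caught indirectly, which leaves 8 − 2 = 6 with no route.
- The indirect route is weak. Item 3 of the Balance Questionnaire asks "Have you had an injury or illness that affects your ability to balance in the past six months", so an older stroke or head injury is caught only if the person reports a balance problem under another item. Section 6 of Appendix 1 mentions conditions affecting neuromuscular control, but that wording is not on the checklist.

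**Is a TMS screen described elsewhere?** Section F.2 names four questionnaires (balance, AII, FAAM, FAAM Sport) and bases eligibility on them. The lists of source documents and study forms (P.1 and P.2) and the visit schedule (Section A) contain no TMS screen. Appendix 1 Section 17 rules out collecting other data before eligibility is determined and consent is signed.

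**Planned TMS exposure.** All three arms are tested.

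- No dropout: 60 × 3 = 180 sessions.
- Planned 10% dropout, all after baseline: 60 × 0.90 = 54, so 60 + 54 + 54 = 168 sessions.

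These figures show how much TMS is planned. They do not estimate how many people would be wrongly admitted, because the documents give no frequency for the eight conditions.

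**AII boundary.** The instrument has nine numbered yes/no items, so scores run from 0 to 9.

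- Inclusion set: {5, 6, 7, 8, 9}.
- Exclusion set as written: {0, 1, 2, 3, 4, 5}.
- Overlap: {5}. One exclusion bars entry, so only {6, 7, 8, 9} can be enrolled.
- With the exclusion changed to fewer than 5, the overlap is empty and {5, 6, 7, 8, 9} can be enrolled, as F.4 intends.

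The same sign is printed in both Section 7 and Appendix 13, so an extraction error is unlikely.

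**FAAM boundaries.** The form has the same overlap at exactly 90% (FAAM-ADL) and 80% (FAAM-S). There the refusal rule agrees with F.4 and A.3.1, which require scores below those values, so nobody's eligibility changes.

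**The case against.** The strongest reply is that part of the screening material cannot be seen. The IRB attachments list "Eligibility Packets_Bio of MT.docx", whose contents are not shown, and the consent pages were removed. A TMS screen may be in either. Section G.1 ties eligibility to the approved IRB protocol, and M.2.b commits the safety plan to it, so A.3.1 applies whatever the checklist omits. F.4 gives the checklist the task of confirming the inclusion criteria, and the form says such a person can, not must, be enrolled. On this reading the form is incomplete, but no one need reach TMS unscreened.

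The likely harm may also be small. A.3.1 does not expect to meet these conditions. The protocol attributes its seizure risk of under 1 in 1,000 to repetitive TMS, which is not used, and signs of seizure lead to withdrawal (A.7.3). The AII slip affects one score, acts before randomisation and cannot bias the comparison between arms. F.4 also makes failing the inclusion criteria an exclusion, so the intent is clear.

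Much of this stands. The documents support the statement that the items are not on the form; they do not show that nobody screens for them. The AII point alone would be a minor correction. But G.1 and M.2.b confirm that A.3.1 binds the trial, which makes its absence from the signed form harder to defend. Even if the packet holds a screen, nothing on the checklist requires it to be completed or negative. A.3.1 also argues its low expectation from an age range of 18 to 35, whereas the trial enrols to 45.

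**Conclusion.** The concern holds, and the checklist must be corrected. It names 0 of the 8 TMS contraindications, and 6 of the 8 have no route on it even by general wording. It also wrongly refuses one AII value, 5.

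The importance rests on the TMS gap. Its practical size is unknown: the documents give no frequency for the eight conditions, and A.3.1 expects few or none among up to 180 planned sessions (168 with the planned dropout). The share of candidates with an AII score of 5 is not given either. The conclusion assumes that the checklist is used as F.4 and Appendix 13 describe. It does not assume that no TMS screen exists elsewhere.

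**What to change.** - Add the eight A.3.1 contraindications to Appendix 1 Section 7, F.4 and Appendix 13, with matching screening questions. The checklist would go from 9 to 9 + 8 = 17 exclusion lines.
- If the eligibility packet already contains a TMS screen, one checklist line is enough: screen completed and negative before enrolment.
- Change the AII exclusion in Section 7 and Appendix 13 to a score below 5.

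Minor tidying in the same revision:

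- Write the FAAM-ADL and FAAM-S inclusion limits as below 90% and below 80%.
- Bring A.3.1 (AII of 4 or more, one giving-way episode) into line with Section 7 (5 or more, two episodes).
- Add self-reported pregnancy to the checklist. The IRB protocol excludes it because it impairs postural control.

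The cost is one revised form, a few extra questions and an IRB modification. No visits are added, and the sample size and analysis do not change.

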To achieve Aim 1, 18 participants per group are needed to ensure significant changes in the primary mechanism of interest following both interventions relative to the control group. Between group (i.e. massage vs. control [$d=0.53$] & mobilization vs. control [$d=0.69$]) pre to post effect sizes from our preliminary data (See Preliminary Studies) were used to calculate the needed sample size. Using GPower (3.1), a repeated measures, between factors ANOVA model for three groups and two time points was used. Parameters included a purposefully conservative intra-measure correlation= 0.90 , $\alpha=0.05$, and $1-\beta=0.90$. To achieve Aim 2, 16 participants per group are needed to identify significant correlations. This value was calculated based on previously established correlations between neuromuscular mechanisms and biomechanical measures of postural control.^{16, 95} Parameters for this analysis included a correlation of $r=0.5$ (range from literature: 0.50 to 0.58), an $\alpha=0.05$, and $1-\beta=0.90$. Thus, we will recruit 20 participants per group and plan for a 10% dropout rate, which would leave 18 subjects per group. Our previous work⁴² had a 98.75% (79/80) retention rate using the same intervention protocol and all participants completed 100% of the treatment sessions.

7 Inclusion & Exclusion Criteria

Inclusion criteria will consist of the following:

- Male or female 18-45 years of age
- History of ankle sprain with at least two episodes of “giving way” within the past six months
- Score of ≥ 5 on the Ankle Instability Instrument (All)
- Score of $\leq 90\%$ on the FAAM-ADL
- Score of $\leq 80\%$ on the FAAM-S.

Exclusion criteria will consist of the following:

- Younger than 18 or older than 45 years
- No history of ankle sprain or episodes of “giving way” in the past six months
- Score of ≤ 5 on the Ankle Instability Instrument (All)

- Score of $\geq 90\%$ on the FAAM-ADL
- Score of $\geq 80\%$ on the FAAM-S.
- An acute ankle sprain within the past 6 weeks.
- Previous history of lower extremity surgery with internal derangements, reconstructions, or repair
- Lower extremity injury within the past 6 months (other than ankle sprains)
- Presence of balance deficits or conditions known to affect balance as noted on the Balance Questionnaire including diabetes and/or vertigo.

8 Randomization Plan

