- People, including children, who are likely to be involved in abusive relationships, either as perpetrator or victim.**
This would include studies that might uncover or expose child, elder or domestic abuse/neglect. ([See SOP Appendix H](#))

A.2.6. If any of the above populations are checked (excluding 'Decisionally impaired individuals' and 'Children who are wards of the State (Foster children)'), please describe your plans to provide additional protections for these subjects.

In all recruitment materials and in the informed consent document, we will include the following language:

What if you are a UNC student?
You may choose not to be in the study or to stop being in the study before it is over at any time. This will not affect your class standing or grades at UNC-Chapel Hill. You will not be offered or receive any special consideration if you take part in this research.

What if you are a UNC employee?
Taking part in this research is not a part of your University duties, and refusing will not affect your job. You will not be offered or receive any special job-related consideration if you take part in this research.

A.2.7. Age range of subjects:

Minimum age of subject enrolled	18
	years
Maximum age of subject enrolled	45
» If no maximum age limit, indicate 99	years

A.3. Inclusion/exclusion criteria

A.3.1. List required characteristics of potential subjects (i.e., inclusion and exclusion criteria). If not covered, list also characteristics that would preclude their involvement.

CAI will be defined as those individuals who: (1) have sustained at least two lateral ankle sprains; (2) have experienced at least one episode of giving way within the past 6-months; (3) answer 4 or more questions of "yes" on the AII; (5) have self-assessed disability scores of <90% on the FAAM; and (6) have self-assessed disability scores <80% on the FAAM-S. These criteria are in agreement with the guidelines established by the International Ankle Consortium's recent position statement.

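### The signed eligibility checklist both includes and excludes an ankle-instability score of exactly 5, so its working cut is 6 where the protocol text admits 5 or more

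*Combined protocol and SAP*

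**What the plan says.** Section 7 of the study protocol has two lines that end in "5 on the Ankle Instability Instrument (All": an inclusion line with an at-or-above sign and an exclusion line with an at-or-below sign. Appendix 13 repeats the pair. It also states how the boxes combine. All inclusion boxes must be ticked and "none of the exclusion criteria are triggered, then the participant can be enrolled in the study"; if "one or more of the exclusion boxes are checked, participation in this study is no longer allowed". The screener signs the form, and then the PI.

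Other places state the score rule differently:

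- F.4, whose criteria are given as following Appendix 13, and K.2.a both ask for "answering 5 or more questions of" Yes. Section 6 also admits 5 and above.
- A.3.1 of the IRB application (Appendix 18) has "answer 4 or more questions of" yes. G.1 cites Appendix 18 as the approved IRB protocol.

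On giving way in the past six months, F.4 and K.2.a require "a history of at least two episodes of" it, and Sections 6 and 7 and Appendix 13 also require two. A.3.1 asks that volunteers "have experienced at least one episode of giving way within the past 6-months", and adds at least two lateral ankle sprains.

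For the two function scores, Section 7 and Appendix 13 include FAAM-ADL at or below 90% and FAAM-S at or below 80%, and exclude scores at or above those same values.

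**The concern.** An inclusion line and an exclusion line on the same score should divide the scale without overlap. Here both claim the value 5, and the form's rule for combining boxes settles the clash by exclusion. F.4 requires every investigator who judges eligibility to complete this form, so the error sits on the document that decides entry. Anyone who follows it correctly turns away people whom F.4, K.2.a and Section 6 admit. At stake is the definition of the enrolled population at its mildest eligible score, and whether a report that quotes the protocol criteria describes the people actually enrolled.

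**Working it through.** No sample size, power or error rate is involved. The check lists every possible score against each rule.

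**Inputs.** Appendix 3 has nine numbered yes/no items per ankle. I assume the score is the number of Yes answers for one ankle, so it is an integer from 0 to 9. The rules are those of Section 7, Appendix 13, F.4, K.2.a, Section 6 and A.3.1.

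**Step 1: the checklist and Section 7.**
- Inclusion set (score ≥ 5): {5, 6, 7, 8, 9}
- Exclusion set (score ≤ 5): {0, 1, 2, 3, 4, 5}
- In both: {5}
- Enrollable = inclusion set minus exclusion set = {6, 7, 8, 9}

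The form is contradictory at 5 but not undecidable, because its closing rule sends a 5 to exclusion.

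**Step 2: all places side by side.**

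| Place | Scores admitted | Minimum | A score of 5 |
|---|---|---|---|
| Appendix 13; Section 7 read the same way | 6 to 9 | 6 | barred |
| F.4, K.2.a, Section 6 | 5 to 9 | 5 | admitted |
| Appendix 18, A.3.1 | 4 to 9 | 4 | admitted |

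**Step 3: FAAM-ADL and FAAM-S.** Inclusion at ≤ 90% and exclusion at ≥ 90% overlap only at exactly 90%; the FAAM-S pair overlaps only at exactly 80%. With any exclusion box barring entry, the form works as < 90% and < 80%. That agrees with F.4, K.2.a and A.3.1. Section 6 says ≤ 90% and ≤ 80%.

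**Step 4: the other differences in A.3.1.** On the score (4 against 5 or 6) and on giving way (one episode against two), the manual is stricter than A.3.1, so it admits nobody whom A.3.1 bars on those two items. The sprain requirement runs the other way. A volunteer with one sprain and two giving-way episodes can pass the checklist but does not meet A.3.1, and no other section requires two sprains.

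**Step 5: size.** The value 5 is one of the five scores (5 to 9) that the inclusion line admits. That counts score values, not people. The documents give no score distribution, so the share removed cannot be computed. Screening comes before the baseline evaluation, and Section 8 places randomisation after it, so the loss occurs before allocation in all three arms.

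**The case against.** The best defence is that the intent is plain. F.4 says that exclusion consists of failing the inclusion criteria plus a list of conditions, so the exclusion lines were meant as complements. F.4, K.2.a, Section 6 and the Section 7 inclusion line all agree on 5 or more. On this view it is one wrong symbol at one score, at one site. That stands as an account of intent and as a limit on the consequence. It does not change what the form does: a screener who applies it as written excludes a 5. The same overlap appears on three scores in two places, so an isolated symbol lost in text conversion is unlikely.

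Appendix 18 can also be defended. It is the initial application of October 2017 and differs from the manual elsewhere: it names REDCap where the manual names Sharepoint, and it says there is no monitoring committee where the manual has one. That explains the drift. But the manual reproduces it and G.1 cites it as approved, so the two still need reconciling.

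A reader might infer that the cut in use is 4, 5 or 6 depending on the page, and that two screeners could classify one volunteer differently. The documents do not support this. The checklist gates every entry, nobody scoring 4 can pass it, and its closing rule gives any two screeners the same answer at 5.

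**Conclusion.** The contradiction is real and can be checked on the page. Section 7 and Appendix 13 list a score of 5 on both sides, and the checklist resolves it to a cut of 6, against 5 or more in F.4, K.2.a and Section 6. The effect is to lose one score value from the enrolled population. Its size in people is unknown, and it does not bias the comparison between arms. The FAAM overlaps are minor. The A.3.1 differences are on paper, and its two-sprain condition is the one that the checklist does not enforce. The score count rests on the assumption that the instrument is scored as Yes answers for one ankle; the overlap at 5 does not.

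Four further inferences go beyond the documents:

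- **That every enrolment at 5 is an eligibility deviation.** This holds only against Section 7 and the checklist; F.4, K.2.a, Section 6 and A.3.1 all admit a 5.
- **That the shift undermines the planning effect sizes.** Section 6 says the criteria match earlier work, but the effect sizes come from preliminary data that the documents do not describe.
- **That the IRB application sets a different age range.** The mention of 18-35 in A.3.1 is an aside about TMS contraindications; A.2.7 sets 18-45, as the manual does.
- **That volunteers already screened out at 5 could be re-checked.** Ineligible people's questionnaires are shredded at once, and the screening log has no column for score or contact.

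This should be corrected. It does not threaten the validity of the trial.

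**What to change.** 1. In Section 7 and Appendix 13, make each exclusion line the exact complement of its inclusion line. If the sponsor confirms that 5 or more stands, the instrument exclusion reads below 5.
2. Choose one strictness for the FAAM-ADL and FAAM-S cuts and use it in Sections 6 and 7, Appendix 13, F.4, K.2.a and A.3.1.
3. In one amendment, reconcile the instrument cut, the giving-way count and the sprain history between A.3.1 and the manual. Which value applies is for the sponsor and investigators to decide; the need is for a single set.

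The cost is wording plus that amendment. Under P.2, changed forms need approval from the monitoring committee and the IRB. Unless the change counts as minor administrative, M.2.c sends it through the independent monitors and the funder before the IRB. No extra participants, visits or measurements are needed. The correction works forward only, so it is worth most if made early in screening.
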